#### *5.2 Study duration*

The study is expected to begin in April 2022 and take 9 months (3 months for enrollment + 6 months total follow up) to complete. Our analysis will take place from December 2022 to March 2023.

#### *5.3 Target population*

Outpatients with advanced cancer at the Ann B. Barshinger Cancer Institute at Lancaster General Health who are eligible for palliative care (see below).

#### *5.4 Accrual*

Patients will accrue to the trial according to their clinician pod in advance of a repeat patient visit. Any eligible patient cared for by an oncology outpatient clinician will be considered eligible.

#### *5.5 Key inclusion criteria*

Patients who meet the following criteria will be eligible for the study.

- Have a functional telephone number
- Receive ongoing care from hematology/oncology services within the Ann B. Barshinger Cancer Institute (ABBCI) at Lancaster General Health.

#### *5.6 Key exclusion criteria*

- Patients appearing for a new patient visit

- Patients who have previously received palliative care
- Patients who are enrolled in an ongoing clinical trial of a therapeutic agent
- Patients who receive primary oncologic care within another institution

## 6. Subject recruitment

Eligible patients will be identified by a Clinical Research Coordinator in advance of a repeat patient visit with an eligible clinician.

## 7. Subject compensation

No compensation will be offered to clinicians in the intervention.

Patients who are administered quality of life surveys and complete a FACT-G survey at 9 weeks or earlier will be offered \$50 at the 9-week timepoint.

## 8. Study procedures

### 8.1 Consent

A waiver of informed consent is requested for the delivery of the palliative care nudge. This is a health system initiative that will be implemented and the study is to evaluate that initiative. Therefore, physicians and their patients will not be consented as this is the standard of practice per the health system initiative and national cancer guidelines. Without a waiver of the consent, the initiative would still be implemented by the health system, but the study would be infeasible. There are several additional reasons why we feel a waiver of consent should be granted. First, it is not feasible to consent every physician and as mentioned this initiative would occur with or without the study of it. Second, if members of the control group were consented, this alone could change their behavior. This could potentially disrupt the design of the study and making interpretation of the findings challenging. Third, physicians are not being forced to refer to palliative care for their patients. Instead, they are receiving behavioral nudges, including default EPIC-based nudges. This is no different than standard of care in which a physician would review the same information and decide to have a palliative care consultation. The initiative is simply a reminder for the physician and makes their standard of care process easier to conduct. Finally, as part of a previous quality improvement initiative, we interviewed nearly 40 clinicians after a trial testing a clinician nudge to perform serious illness conversations. We found no evidence of harm and found that serious illness conversations were considered standard of care for patients with cancer.

Patients who are selected for quality of life surveys will be consented over the phone for administration of FACT-G surveys at baseline (prior to hospital discharge) and at 3, 6, 9, and 18 weeks after enrollment. A copy of the informed consent form is available (**Appendix B**). Those who elect not to participate will be asked to grant permission (or not) for the study team to

collect limited data from them. An abbreviated Study Decline Consent form will be utilized for this purpose (**Appendix C**).

### *8.2 Procedures*

Baseline data on oncologists and their patients at Lancaster General Health will be obtained from Penn Data Store and Clarity (Epic's data reporting database). Physician data includes demographic information (e.g. sex, type of medical degree, etc.) and may be also obtained from publicly available databases or websites online. Baseline data collected on patients will include age, gender, zip code of residence, type of cancer, Elixhauser comorbidity index, ECOG performance status, whether the patient is on active systemic therapy, and understanding of palliative care. This will be collected via the electronic health record and an in-person enrollment questionnaire (**Appendix D**) upon enrollment into the trial. Those who elect not to participate, but consent to limited data collection, will be asked to fill out a similar questionnaire including reason(s) for not wanting to participate in a de-identified manner (**Appendix E**).

Prior to the trial, staff will randomize each clinician pod in a 1:1 fashion to either intervention or usual care. The Principal Investigator ([name]) will be blinded to arm assignment. In both intervention and control arms, research coordinator staff will identify patients with advanced cancer who are actively cared for within the Ann B. Barshinger Cancer Institute system. They will then regularly review the electronic health record for eligible clinicians to identify patients with an upcoming repeat patient visit who are eligible for palliative care. Patients who are eligible will have a solid malignancy and at least one of the following five conditions: (1) Documented advanced (stage IV) solid malignancy; (2) Known central nervous system metastasis, (3) Eastern Cooperative Oncology Group performance status  $> 2$ , Karnofsky Performance Status  $< 50$ , (4) uncontrolled symptoms such as pain, escalating opioids, nausea/vomiting, distress, dyspnea, delirium, or (5) hospitalization relevant to cancer or treatment.

For patients whose clinician pods are randomized to the intervention arm, the care team pod will receive an EPIC in-basket message indicating that the patient is eligible for Palliative Care and that a default referral order has been pended for that patient. Clinicians will be given an opportunity to respond if they do not want their patient to be referred to palliative care. For clinicians who do not respond, after the allotted time, the Clinical Research Coordinator will reach out to the patient to introduce palliative care and ask if ABBCI staff can schedule an appointment. For non-English speaking patients, an interpreter will assist research staff. For clinicians who respond no, the pended order will be removed and no patient contact by the research team will occur.

For eligible patients whose clinician pods have been randomized to the control arm, no intervention will be provided. Clinicians will refer patients to palliative care based on their usual practice.

Among patients in the intervention arm for whom palliative care referral is placed, who accept for a scheduler to call them to make an appointment, a trained research coordinator will approach 40

patients as a convenience sample to administer a baseline FACT-G survey (**Appendix A**). 40 randomly selected patients, matched on categories including age category and type of cancer, will be selected from the pods not receiving the intervention. For patients that choose to enroll in the survey component, a baseline FACT-G survey will be administered prior to discharge in-person via paper or electronically. Surveys will be repeated at 3, 6, 9, and 18-week intervals by either telephone or in-person at an in-person visit. For patients that complete the 9-week survey or any survey prior, a \$50 gift card will be given at the 9-week time point. Patients who miss their visits with palliative care will be contacted by the coordinator to identify why (**Appendix F**) and reschedule the appointment.

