## 9. Analysis plan

We will use REDcap, a HIPAA-compliant and secure database tool, to track all components of the study. Descriptive statistics will be used to estimate the frequencies, means, and standard deviations of the study variables. Differences between study groups in baseline characteristics and clinical outcomes will be assessed with the use of two-sided Fisher's exact tests and chi-square tests for categorical variables and independent-samples Student's t-tests for continuous variables. The unit of analysis will be the patient.

The primary study endpoint is a binary patient-level variable indicating completion of a palliative care visit within 24 weeks of the clinician behavioral nudge. This analysis will be conducted as a time-to-event analysis among all eligible advanced cancer patients. Cox proportional hazard regression analyses, adjusted for baseline covariates, will be used to examine the effect of nudges on completion of palliative care consultation for advanced cancer patients. Competing risk caused by patients who die within 24 weeks will be considered as censored in the analysis. Covariates will include patient and cancer-related variables. Patients will be followed for 24 weeks or until death. Using a longitudinal multilevel mixed-effects model with clustering by discharging clinician (intraclass correlation coefficient 0.5 based on prior randomized trial); a two-sided type I error rate of 0.05; and a baseline palliative care visit rate of 45% (standard deviation 10%), we expect that a sample size of 250 patients will give us 80% power to detect a meaningful 34 percentage point response in palliative care visits, considering the presence of a competing risk of 6-month mortality at 20%.

One secondary outcome will be (1) change in quality of life between 0 and 9 weeks (as measured by the Functional Assessment of Cancer Therapy – General (FACT-G) among patients who receive palliative care compared to matched controls. Multivariate linear regression analyses, adjusted for baseline scores, will be used to examine the effect of palliative care on completion of palliative care consultation for advance cancer patients. For intention-to-treat analyses, we will use the conservative method of carrying the most recent quality-of-life values forward to account for all missing data, including data that are missing owing to death.

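### Four of the five qualifying conditions are not among the listed baseline data, and the all-patient binary outcomes have only unadjusted tests, so a difference in patient mix between randomised pods could remain in those estimates

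*Combined protocol and SAP*

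**What the plan says.** Section 8.2 requires a solid malignancy and "at least one of the following five conditions: (1) Documented advanced (stage IV) solid malignancy; (2) Known central nervous system metastasis". The third condition is poor performance status, and the last two are "uncontrolled symptoms such as pain, escalating opioids, nausea/vomiting, distress, dyspnea, delirium, or (5) hospitalization relevant to cancer or treatment".

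The same section gives the baseline data: "Baseline data collected on patients will include age, gender, zip code of residence, type of cancer, Elixhauser comorbidity index, ECOG performance status", followed by "whether the patient is on active systemic therapy, and understanding of palliative care". The sources are the electronic record and an enrolment questionnaire (Appendix D).

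For the primary outcome, Section 9 states: "Cox proportional hazard regression analyses, adjusted for baseline covariates, will be used to examine the effect of nudges". It describes the covariates only as patient-level and cancer-related, without naming any. Survival also gets a covariate-adjusted Cox model, and FACT-G is adjusted for the baseline score.

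No model is given for 30-day emergency and hospital use or for documented advance care planning. They fall under the general sentence in Section 9: "Differences between study groups in baseline characteristics and clinical outcomes will be assessed with the use of two-sided" Fisher's exact and chi-square tests if categorical, and t-tests if continuous. Section 3.3 lists these outcomes as exploratory; Section 9 lists them as further secondary outcomes.

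Staff randomise pods 1:1 before the trial, and coordinators then screen for eligible patients (Section 8.2). Neither stratification of pods nor the number of pods is stated.

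**The concern.** The qualifying conditions describe patients at very different points in their illness. Someone with stable stage IV disease and someone recently hospitalised with uncontrolled symptoms can both be eligible. They probably differ in their chance of a palliative care visit under usual practice, in acute care use and in survival. Section 4 points the same way: it says that palliative referral often happens in hospital for acutely ill patients, and that underestimating symptom burden or mortality risk delays referral.

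The unit of randomisation is the pod, so a modest number of pods decides how similar the arms are. If pods differ in case mix, the arms can differ by more than they would under patient-level randomisation. Screening also follows randomisation. The principal investigator (Sections 8.2 and 11.2) and the analyst (Section 11.2) are to be blinded, but the coordinators are not said to be. Whether symptoms are uncontrolled is partly a judgement, so screening could drift apart between arms.

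If the conditions are not stored, such a difference can be neither shown nor adjusted for. It matters most for the all-patient binary outcomes, whose stated tests use no covariates at all.

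**Working it through.** **1. Conditions against listed baseline data (both in Section 8.2)**

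| Qualifying condition | Counterpart in the baseline list |
|---|---|
| Stage IV solid malignancy | none (cancer type only) |
| CNS metastasis | none |
| Poor performance status | ECOG performance status |
| Uncontrolled symptoms | none |
| Cancer-related hospitalisation | none |

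Four of five have no counterpart.

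**2. Adjustment by outcome (Section 9)**

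- Primary visit outcome and survival: Cox models with unnamed baseline covariates.
- FACT-G: baseline score.
- 30-day acute care and advance care planning: none. Section 9 mentions a multilevel model with clustering by clinician, but only in the sample size sentence for palliative care visits.

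**3. The plan's own power figure**

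Section 9 gives 80% power with 250 patients, 45% against 79% (45 + 34), ICC 0.5 and two-sided alpha 0.05. Without clustering, 31 per arm are needed. With 125 per arm, the design effect that leaves 80% power is 125/31 = 4.03. Setting 1 + (m − 1) × 0.5 = 4.03 gives m of about 7 patients per cluster, or about 35 clusters. The pod count is not given, so the 80% can be neither confirmed nor refuted. The present point does not depend on it; only the cluster size of 7 is used, in step 5.

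**4. How far the mix could differ by arm**

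These inputs are assumptions: prevalence p = 0.50 for a condition, k pods of m patients (250/k, rounded down), and a between-pod ICC ρ of that condition from 0 to 0.10.

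SD of the between-arm difference = √{2 p(1 − p)[1 + (m − 1)ρ] / (mk/2)}

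For 4 pods of 62 and ρ = 0.10: √(0.5 × 7.1 / 124) = 0.169, or 16.9 points.

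If the condition shifts a binary outcome's risk by 20 points (assumed), the unadjusted difference moves by 0.20 × the imbalance. Simulation with 20,000 draws per row, in percentage points except the column of chances:

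| Pods | ρ | SD of imbalance | Chance of imbalance above 10 points | Displacement, 1 SD | Displacement, 95th percentile |
|---|---|---|---|---|---|
| 4 | 0 | 6.4 | 12% | 1.3 | 2.6 |
| 4 | 0.05 | 12.8 | 44% | 2.6 | 5.0 |
| 4 | 0.10 | 16.9 | 56% | 3.4 | 6.6 |
| 8 | 0.05 | 10.1 | 32% | 2.0 | 4.0 |
| 8 | 0.10 | 12.7 | 43% | 2.5 | 5.0 |
| 20 | 0.05 | 8.0 | 21% | 1.6 | 3.2 |
| 20 | 0.10 | 9.3 | 28% | 1.9 | 3.7 |

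**5. Precision gained by adjustment**

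For independent patients, covariates explaining a share R² of the variance are worth 1/(1 − R²) − 1 more patients: 11% at R² = 0.10 and 25% at 0.20 (both assumed). Here patients are clustered. The variance of a cluster mean, in units of total variance, is ICC + (1 − ICC)/m. With ICC 0.5 and m = 7 this is 0.5 + 0.5/7 = 0.571. If covariates explain 20% of the within-cluster part only, it becomes 0.5 + 0.4/7 = 0.557, a reduction of about 2.5%. Larger clusters gain less, unless the covariates also explain differences between pods.

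**The case against.** A reader might infer that the Cox models leave the qualifying conditions out and that known prognostic differences between the arms therefore stay in all the effect estimates. The documents do not support this, for three reasons.

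- Section 9 names no covariates. Stage and CNS disease are cancer-related variables and could well be included. For the Cox models the gap is one of specification, not a shown omission. ECOG status, comorbidity, cancer type and systemic therapy would also carry part of the information.
- Non-collection is not proved. The baseline list need not be exhaustive, eligibility is read from the electronic record, and Appendix D is not in the text available for this review.
- No difference between arms is reported. Chance imbalance between randomised pods adds variance, not bias in expectation. A bias argument has to rest on identification after randomisation, which makes bias possible but does not show it.

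The remedy also has limits. Eligibility needs only "at least one of the following five conditions", so a screener may stop at the first one found; recording all five is some extra work. Adjusting for a symptom judgement that is made differently by arm could add bias. A regression without a pod term would still ignore the clustering.

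All of this stands. It narrows the point and shapes the fix. It does not rescue the unadjusted, unclustered tests, which are the only method stated for the all-patient binary outcomes.

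**Conclusion.** The concern holds in a limited form. Four of the five conditions have no place in the listed baseline data, the covariates are unspecified, and the all-patient binary outcomes are tested without adjustment. If the mix of conditions differs by arm, that difference would pass into those unadjusted estimates; the Cox models may absorb part of it.

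The size rests on assumptions, because the documents give neither the number of pods nor the prevalence or effect of any condition. With 50% prevalence and a 20-point shift in risk, the displacement is about 1 to 3 points at one SD, and close to 7 points at the 95th percentile in the least favourable case examined (4 pods, ρ = 0.10). These figures apply to unadjusted comparisons. They should not be read as bias in the primary outcome, which has an adjusted analysis and a planned effect of 34 points. Nor should a precision gain of 11 to 25% be expected: if clustering is near the stated ICC of 0.5, the gain is far smaller. The main return is protection against imbalance and the ability to show it.

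**What to change.** - Record each of the five conditions as yes/no at screening, in both arms, and tabulate them by arm.
- Name the covariates in Section 9. Add stage IV, CNS metastasis and recent cancer-related hospitalisation to the listed baseline variables in the primary and survival Cox models. Use the symptom item only in a sensitivity analysis.
- Replace the unadjusted tests of 30-day acute care and advance care planning with a regression on the same covariates that accounts for pod, by a random effect or by cluster-robust errors with a small-sample correction. Report an adjusted risk difference.
- Reconcile Sections 3.3 and 9 on whether these outcomes are exploratory or secondary.

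The cost is a few REDCap fields, a screener who checks all five conditions, and slightly more analysis work. The primary model can carry three more binary covariates: the planned rates imply 125 × (0.45 + 0.79) = 155 visits, or about 124 after a 20% loss. Survival has less room, at about 0.20 × 250 = 50 deaths by six months, so its covariate list should be short and fixed in advance.

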## 5. Study design

### 5.1 Design

This is a 2-arm pragmatic randomized trial among approximately 250 outpatients with advanced cancer to assess response to behavioral nudges to refer to palliative care. The setting will be outpatient oncology at the Ann B. Barshinger Cancer Institute at Lancaster General Health. Eligible clinicians will be randomized in clusters by overlapping clinical team (pod) to receive default EPIC-based prompts for palliative care referral among advanced cancer patients (Arm 1) vs no intervention/usual practice (Arm 2). These nudges have been shown to positively influence clinician behavior and are often used to drive value-based oncology care; however, they have never been studied in the context of palliative care referral. The primary outcome is completion of a palliative care referral within 12 weeks of enrollment.

Following the intervention, brief REDCap questionnaires will be sent to all clinicians who participated in the trial to explore perceptions of the study intervention. This survey should take no longer than five minutes for clinicians to complete and will assess their feedback on the overall intervention in addition to specific components including automated identification of patients, receiving text and email notifications, and identifying the appropriate patients. The survey will also collect basic demographic information (age, gender, practice site, and comfort with SICs) (**Appendix 3**).

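### Eligibility is probably judged with the pod's arm known, and two of the five entry conditions are left to judgement, so patient entry could differ by arm

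*Combined protocol and SAP*

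**What the plan says.** Allocation comes first. Section 8.2 states: "Prior to the trial, staff will randomize each clinician pod in a 1:1 fashion to either intervention or usual care". Patient identification follows, in both arms: "research coordinator staff will identify patients with advanced cancer who are actively cared for", and then "They will then regularly review the electronic health record for eligible clinicians to identify patients with an upcoming repeat patient visit". Section 6 repeats this and names the role: "Eligible patients will be identified by a Clinical Research Coordinator in advance of a repeat patient visit with an eligible clinician".

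In intervention pods, if the clinician does not respond in the time allowed, "the Clinical Research Coordinator will reach out to the patient to introduce palliative care and ask if ABBCI staff can schedule an appointment" (Section 8.2). Section 8.2 blinds the principal investigator, and Section 11.2 blinds the principal investigator and the statistical analyst. No blinding of coordinators is described, and no split between those who identify patients and those who contact them.

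A patient with a solid malignancy enters on any one of five conditions (Section 8.2). The first three are stage IV disease, central nervous system metastasis and poor performance status. The fourth is "uncontrolled symptoms such as pain, escalating opioids, nausea/vomiting, distress, dyspnea, delirium" and the fifth is "hospitalization relevant to cancer or treatment".

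The baseline data listed in Section 8.2 include age, cancer type, comorbidity index, ECOG status and active systemic therapy. They do not include symptom burden or the condition on which the patient qualified. Section 9 analyses all eligible patients in a Cox model adjusted for patient and cancer-related covariates that it does not name.

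**The concern.** Randomising pods makes the pods comparable. The patients inside them are comparable only if they are found in a way that does not depend on the arm. Here the allocation is fixed before screening starts. It applies to a whole pod, so anyone who has handled one intervention patient knows the arm of every later patient in that pod.

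Conditions 1 to 3 rest largely on recorded facts. Condition 4 gives examples without a scale, threshold or look-back period. Condition 5 has no time window and leaves relevance to the reader of the chart. A coordinator who knows the arm could, without intending to, apply either one more readily in some pods than in others. Because the primary analysis takes all eligible patients, that judgement sets its denominator. A difference in case mix would then be read as an effect of the nudge, or would hide part of one. As the qualifying condition is not listed for collection, the report could not show whether this had happened.

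**Working it through.** The plan gives no figure on this point, so there is none to reproduce. The check has two parts.

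**Sequence and knowledge of the arm**

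| Step | Who | Arm known? |
|---|---|---|
| Pods randomised before the trial (8.2) | Staff | Fixed from here on |
| Records reviewed, eligibility judged (6, 8.2) | Coordinator | Not stated to be blinded |
| Message to care team, intervention pods (8.2) | Sender not named | Yes |
| Call to patient if no opt-out, intervention pods (8.2) | Coordinator | Yes |

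The same role appears at the second and fourth steps. Different people could fill it, but no such division is described. Knowledge of the arm at the second step is therefore probable, not certain.

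**Possible size, with no nudge effect**

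Let *s* be the share of an arm's patients who meet none of conditions 1 to 3 and so entered on 4 or 5. Let *b* be their visit probability and *a* that of all other patients. An arm's visit rate is *s·b* + (1 − *s*)·*a*. With *a* and *b* the same in both arms, the spurious difference is

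(*s*₁ − *s*₀) × (*b* − *a*).

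The documents give none of these quantities. Assumed ranges are 0.05 to 0.20 for the difference in share and 0.15 to 0.30 for the difference in visit probability.

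- Low end: 0.05 × 0.15 = 0.0075, or 0.75 percentage points.
- High end: 0.20 × 0.30 = 0.06, or 6 percentage points.

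If the 250 patients split evenly, 125 per arm, the difference in share amounts to 0.05 × 125 ≈ 6 patients at the low end and 0.20 × 125 = 25 at the high end. Against the planned 34 points (Section 9), the bias is 0.75/34 ≈ 2% to 6/34 ≈ 18%.

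A harsher set of assumptions keeps the control visit rate at the plan's 45%. It puts *s*₀ at 0.20, *s*₁ at 0.30 to 0.50, and *b* at 0.55 to 0.75. Then *a* = (0.45 − 0.20*b*)/0.80.

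- *b* = 0.55: *a* = 0.425, and the smallest bias is 0.10 × 0.125 = 1.25 points.
- *b* = 0.75: *a* = 0.375, and the largest bias is 0.30 × 0.375 = 11.25 points.

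Either factor can be negative, so the bias can run in either direction. The calculation is on the scale of visit proportions, and the planned analysis is a Cox model, so it indicates size only.

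**The case against.** The plan has real protections. The same conditions apply in both arms. Section 5.4 counts any eligible patient of an oncology clinician, so coordinators are told to identify patients, not to pick among them. Consent to the nudge is waived (Section 8.1), which removes differential consent, a common route to selection in cluster trials. Discretion alters entry only for patients who meet none of the recorded conditions. In a population first identified as having advanced cancer, these may be few. The model adjusts for patient and cancer-related variables, and ECOG status, comorbidity and systemic therapy are collected.

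All of this stands and limits the risk. It does not remove it. Counting every eligible patient does not help where eligibility is itself the judgement, and the model cannot adjust for symptom burden or route of entry if neither is collected. Section 5.1 does list automated identification of patients among its clinician-survey topics, but Sections 6 and 8.2 describe coordinator review. Those sections should be reconciled.

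A reader might go further and infer that coordinators favour patients receptive to palliative care. The documents do not support that: eligibility is set from the record, and the patient is contacted only after the opt-out period (Section 8.2, Appendices 1 and 2). Nor would unequal numbers per arm bias a comparison of rates by themselves. At most they would be a sign of selection.

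**Conclusion.** The concern holds as a risk in the design. Eligibility is probably judged with the arm known, conditions 4 and 5 are not defined tightly enough to prevent differential use, and the listed data could not reveal or correct it. The direction is unknown. The size is 0.75 to 6 percentage points under the main assumptions and up to about 11 under harsher ones. None of these inputs comes from the documents.

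A reader might infer that selection has occurred, or that it could account for the planned effect. Neither follows. The documents show an opening for selection, not its use, and every value computed is well below 34 points. The bias would matter more if the observed effect were smaller than planned, and enrolling more patients would not reduce it.

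**What to change.** 1. Identify patients on conditions 1 to 3 by one fixed health-record query, run identically in all pods.
2. Accept conditions 4 and 5 only on a documented chart entry that meets a definition written before enrolment starts.
3. Record every qualifying condition for each patient in REDCap, with a date stamp, before any message is sent, and at the corresponding time in control pods.
4. Analyse all identified patients by the randomised arm of their pod.
5. Report numbers screened, numbers eligible and qualifying conditions by arm.
6. Add a sensitivity analysis of the primary outcome limited to patients who meet at least one of conditions 1 to 3.

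The date stamp documents the judgement but does not blind it, since a pod's arm is known after its first patient. Most of the protection comes from the query, the written definitions and the restricted analysis.

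The cost is some query set-up and data entry. Clarity and REDCap are already in use, and no extra staff or patients are needed. Patients with undocumented symptoms may be missed, in both arms alike, and the sensitivity analysis will be less precise than the main one.
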